**Table 7.1.18. Change in Impact on Parents/Caregiver**

Domain	Baseline	Week 12	CFB in proportion at Week 12	p-value
	(N=xx)	(N=xx)	(N=xx)	
Q2: Do you feel that you understand your child's acne-related concerns?				
Not at all / A little	n (%)	n (%)	%	p
Quite a bit / Very much	n (%)	n (%)	%	p
Somewhat	n (%)	n (%)	%	
Q3: Over the past 7 days, how concerned have you been about your child's acne?				
Not at all / Slightly	n (%)	n (%)	%	p
Moderately / Extremely	n (%)	n (%)	%	p
Somewhat	n (%)	n (%)	%	
Q4: How concerned are you about your child's ability to accomplish future goals and reach full potential due to acne?				
Not at all / Slightly	n (%)	n (%)	%	p
Moderately / Extremely	n (%)	n (%)	%	p
Somewhat	n (%)	n (%)	%	

Note: X patients had missing data; The denominator for the percentage is the number of patients with available data (N=X)

## 7.2 Tables from clinician's DCF (FAS Population)

Clinician data is analyzed using the FAS dataset. In relevant instances (such as IGA and physician satisfaction evaluations), only FAS dataset with corresponding week 12 clinician data is used. All data tables in this section correspond to FAS population.

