## 7.6 Early Termination Encounter (Encounter # x)

Site Investigators will attempt to follow the progress of every subject admitted to the study through to study completion. If a subject fails to complete requested study procedures (i.e., completion of online surveys), a reasonable effort will be made to contact the subject and ascertain the reason(s) for non-compliance with study procedures.

If a subject does not complete the study for any reason (including Investigator discretion), the reason and circumstances for the subject's early termination will be fully documented; if possible, the assessments specified for the forthcoming (next) study encounter will be performed.

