## 11 DATA MANAGEMENT

The study data portal will comprise of two distinct, linked data sources, one being the traditional EDC containing eDCF to gather data from Site Investigators; another being the mobile App that gathers data directly from study Subjects. The back-end EDC platform will be programmed with edit checks to ensure that the incoming data from Site Investigators and Subjects are routinely checked for data quality, any systematic missing data, trends in select outcome measures and safety events.

A centralized data review strategy will ensure consistency, integrity, logical completeness, and coding of collected data. Queries will be generated for study sites to solicit additional required information, as needed. Any necessary data corrections in the EDC portal at the back-end will be made by the central research staff, and ratified by the CRO Program Lead for appropriateness and correctness.

Incoming AE data will be routinely checked to flag SAEs and other pertinent high-priority safety events, gather additional information from the sites (as/if needed), and additionally collected information will be integrated back with the master study dataset, while the safety data is processed for expedited reporting to study sponsor.

Any additional quality assessment(s) will be carried out for the study per the study specific data management plan. Following completion of all data review activities for all patients, records within the master dataset will be locked, followed by completion of medical coding for concomitant medications and adverse events and preparation of dataset for statistical analyses.

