## 6 STATISTICAL CONSIDERATIONS

### 6.1 Sample Size Considerations

No formal sample size and power calculations were undertaken. Considering the descriptive nature of the study and the feasibility of recruiting the study population, approximately 300 study Subjects from across a maximum of 40 clinical sites for the entire study has been identified as a sample to guide the planned analysis addressing the study objectives. It is expected that there will be Subject attrition during the course of the study.

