### 6.2 Analysis Populations and Datasets

Statistical analysis and data tabulation will be performed using the following analysis populations unless specified otherwise:

- **Safety Population:** All patients who received at least one dose of sarecycline during the study observation period, as part of usual care. This in essence constitute all 300 Subjects recruited into the study.
- **Full Analysis Set (FAS):** All patients within the Safety Population that had at least one question answered pertaining to study primary research objective. This in essence will constitute all Subjects who completed their Week-12 survey. By definition, this would exclude all Subjects who were terminated (for any reason) at any timepoint (prior to Week-12) in the study.

In the event that the safety population and FAS differ, all safety evaluations (part of additional objectives) will be conducted among the safety population, while FAS will be used to conduct

analyses addressing rest of the study objectives, including the description of population demographics, primary and secondary objectives, and select additional (non-safety related) objectives.

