patients reporting “Quite a bit/Very” at Week-12, to compute respective P values. Continuous measures will be assessed using summary statistics; paired sample t-tests will be used to assess statistical differences for CFB evaluations, while independent sample t-tests will be used to assess statistical differences between different patient groups (for subgroup analysis) for a given measure at a particular timepoint (such as Baseline or Week-12).

Computation of statistical differences will be performed only as an exploratory step (and not for hypothesis testing), considering the descriptive nature of the study; for such exploratory evaluation, P value  $\leq 0.05$  will be considered significant. All statistical analyses will be based on all available data assuming that all missing data are uninformative and will be conducted using appropriate statistical software, such as SAS.

An interim analysis will be conducted using FAS, upon completion of 12 weeks of data collection (from both patients and clinicians) for ~200 study Subjects, using the statistical methods identical to the analyses planned for FAS-based final data analyses; the focus of the interim analyses will be the primary objective, secondary objective and select additional objectives, as outlined below; no subgroup analyses will be considered.

- FAS cohort demographics
- PROs: Antibiotic attitudes at baseline
- PROs: CFB in EPQ measures
- PROs: CFB in ASIS measures
- PROs: CFB in Patient Acne Severity and How Face Looks (with and without LOCF imputation)
- PROs: CFB in Parent/caregiver concerns about the child with Acne:
  - Understanding child's concerns
  - Concerned about child's acne
  - Concerned about child's ability to accomplish future goals
- Facial IGA and Facial IGA success (with and without LOCF imputation)
- Select comparison of patient and clinician reported measures: Acne Severity (with LOCF imputation)

- Select comparison of pediatric patient and caregiver reported measures:
  - Understanding child's concerns
  - Concerned about child's acne
  - Concerned about child's ability to accomplish future goals
- Clinician satisfaction with sarecycline
- Sarecycline treatment characteristics

The description of the individual study measures are outlined in the forthcoming sections.

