## 6.5 Secondary Endpoint Analysis

The secondary endpoint of the study is the proportion of Subjects with Facial IGA success at Week 12, defined as  $\geq 2$ -point decrease in IGA score from baseline and a score of 0 (clear) or 1 (almost clear) at Week 12. The analyses of IGA success will be conducted for the overall cohort (using the FAS dataset). LOCF data imputation method will be used to impute responses at Week 12 for the Subjects with missing data at Week 12. Relationship between this endpoint (with LOCF imputation) and subject characteristics will be explored using descriptive analyses, by leveraging subgroup analysis outlined in Section 6.3.2.

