## 6.6 Additional Analysis

### 6.6.1 Treatment Satisfaction Analyses

Investigator's global satisfaction with sarecycline treatment will be analyzed using data at Week 12 from a single question: "how satisfied are you with sarecycline treatment outcomes", with response options ranging from 'Very Satisfied' to 'Very Dissatisfied'. Frequency of responses will be tallied for all Subjects. Proportion of Subjects for whom Investigators indicated 'Very Satisfied' or 'Satisfied' will be reported.

The analyses will be done for the overall cohort, using FAS, and stratified by age and other relevant subgroups outlined in Section 6.3.2. Relationship between Investigator satisfaction and subject characteristics will be explored using descriptive analyses.

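### Facial IGA success and investigator satisfaction are analysed only in subjects who completed the Week-12 patient survey, so any Week-12 investigator rating made without a survey would be left out

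*SAP*

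**What the plan says.** SAP 6.2 opens the FAS definition with treated subjects who answered at least one question bearing on the primary objective. It then fixes the meaning in practice: "This in essence will constitute all Subjects who completed their Week-12 survey". Subjects terminated before Week 12 are excluded. SAP section 7 repeats the rule, tying membership to the Week-12 survey. That survey is taken by online portal or app, with a caregiver answering as proxy at ages 9-11.

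The same set is then applied to endpoints that the patient does not report:

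- SAP 6.5, IGA success: "The analyses of IGA success will be conducted for the overall cohort (using the FAS dataset").
- SAP 6.6.1, investigator satisfaction: "Frequency of responses will be tallied for all Subjects", with the following paragraph naming the FAS as the population.
- SAP 7.2, all clinician tables: "Clinician data is analyzed using the FAS dataset". For IGA and satisfaction, 7.2 also requires Week-12 clinician data.

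Protocol section 11 describes two linked but distinct sources. One is the EDC with the investigators' eDCF, "another being the mobile App that gathers data directly from study Subjects". Protocol 12.2 defines the FAS more loosely, as treated subjects with some data on the primary objective, and states no Week-12 survey condition.

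**The concern.** Membership of the FAS depends on one respondent and one instrument, the patient's survey. IGA and satisfaction come from another respondent and another form. If a subject attends Week 12, is rated by the investigator and does not complete the survey, nothing is missing for either investigator endpoint, yet the rule removes the rating.

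The secondary objective is the effectiveness of sarecycline by IGA among treated patients. Under the rule, the planned estimate is conditional on the patient having answered a questionnaire after 12 weeks. If answering is related to outcome, the reported proportion is shifted. The selection serves a purpose where patient and clinician answers are paired (SAP 7.3). It serves none where the investigator's rating stands alone, and the SAP gives no reason for it there.

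**Working it through.** **Is there a planned figure to reproduce?** No. SAP 6.1 says "No formal sample size and power calculations were undertaken", and neither document assumes a success rate, a satisfaction rate or a rate of survey non-response. The check is therefore a trace of the definitions, followed by an illustration of size.

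**Step 1: the rule applied to the four possible Week-12 cases** (SAP 6.2, 6.5, 6.6.1, 7 and 7.2 read together).

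| Patient survey | Investigator rating | In the IGA and satisfaction tables? |
|---|---|---|
| yes | yes | yes |
| yes | no | in the FAS, but removed by the second condition in 7.2 |
| no | yes | no, although the endpoint was observed |
| no | no | no |

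The third row is the point at issue.

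**Step 2: can the third row occur?** Yes, under the plan as written. The sources are separate (Protocol 11), and Protocol 7.5 has the investigator and the subject complete their Week-12 items independently. Protocol 7.6 provides for the event: "If a subject fails to complete requested study procedures (i.e., completion of online surveys"). How often it occurs is not stated.

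**Step 3: does another analysis recover the rating?** No. SAP 6.11 and 7.5 list results with and without LOCF, and a split by visit type. All stay within the FAS. LOCF cannot help, because the rating is observed and its subject is outside the dataset. Read strictly, the second condition in 7.2 also leaves LOCF little or nothing to impute at Week 12, so the comparison with and without LOCF says little about who was left out.

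**Step 4: illustration of size.** Let m be the share of rated subjects with no Week-12 survey, pF the success rate in the FAS, and pO the success rate among the excluded ratings.

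- All-rated proportion = (1 - m) × pF + m × pO
- FAS minus all-rated = m × (pF - pO)

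Neither m, pF nor pO is in the documents. Assume pF = 60% and, for the counts only, that all 300 subjects have a Week-12 rating. At m = 10%:

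- pO = 0: 0.90 × 60% + 0.10 × 0% = 54.0%, a difference of +6.0 points.
- pO = 30%: 0.90 × 60% + 0.10 × 30% = 57.0%, a difference of +3.0 points.
- pO = 60%: no difference.
- pO = 100%: 0.90 × 60% + 0.10 × 100% = 64.0%, a difference of -4.0 points.

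| m | Ratings excluded | n analysed | All-rated if none succeed (difference) | All-rated if all succeed (difference) |
|---|---|---|---|---|
| 5% | 15 | 285 | 57.0% (+3.0) | 62.0% (-2.0) |
| 10% | 30 | 270 | 54.0% (+6.0) | 64.0% (-4.0) |
| 15% | 45 | 255 | 51.0% (+9.0) | 66.0% (-6.0) |

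The end columns are bounds, not expectations.

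**Step 5: precision.** The 95% half-width is 1.96 × √(0.6 × 0.4 / n). This gives 5.5 points at n = 300 and 5.8 points at n = 270, so the issue is selection and not lost precision.

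**The case against.** The strongest case for the plan is that one analysis set for all non-safety objectives is an open and common choice. SAP 6.2 assigns the FAS to the secondary objective in plain terms, and Protocol 12.2 also uses its FAS for everything except safety. The study is descriptive, and SAP 6.3.1 says "Computation of statistical differences will be performed only as an exploratory step (and not for hypothesis testing". Subjects are paid for surveys and may be sent reminders (Protocol 6.3.2), and Protocol 7.6 requires an effort to contact those who do not complete them, so the affected group may be small or empty. All of this stands. It limits the importance of the point but does not give a reason for the rule.

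Three stronger readings are tempting, and the documents do not support them.

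- *The SAP contradicts itself.* A reader might set the phrases about the overall cohort (6.5) and all subjects (6.6.1) against the survey-based set. Both sections name the FAS in the same place. Overall is most naturally read as the contrast to the subgroups of 6.3.2.
- *Observed data are certain to be lost.* They are lost only if at least one rated subject has no survey. Protocol 7.6 treats survey non-completion under early termination, and SAP 6.2 mentions only terminated subjects as falling outside the FAS.
- *IGA success is overstated.* That needs excluded subjects to have done worse, which no passage shows. The shift can go either way.

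The comparison with the protocol also needs care. Protocol 12.2 states no Week-12 survey condition, and if baseline answers count as some data, these ratings would stay in. But the primary endpoint is PROs at Week 12, so a narrower reading of the protocol is possible.

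**Conclusion.** The point holds as a conditional one. Followed exactly, the SAP excludes any Week-12 IGA or satisfaction rating from a subject who did not complete the survey, and no planned analysis brings it back. Neither the number of such ratings nor the direction of the shift can be taken from the documents. The range of +6 to -4 points rests on an assumed 10% exclusion and an assumed 60% success rate in the FAS, with the excluded subjects at the two extremes. The counts in the table also assume that all 300 subjects are rated at Week 12. SAP 6.1 expects attrition, so actual counts for a given m would be lower, although the differences in points depend only on m, pF and pO. Investigator-reported safety data are not affected, because they use the Safety Population. The change is worth making because it removes an avoidable selection on the secondary endpoint at almost no cost.

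**What to change.** Amend SAP 6.2, 6.5, 6.6.1 and 7.2 so that IGA success and investigator satisfaction are analysed in Safety Population subjects whatever their survey status.

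- **Tables without imputation and satisfaction tables** (7.2.4.1-7.2.4.3, 7.2.8, 7.2.9): use every observed Week-12 investigator rating.
- **LOCF tables** (7.2.4.4-7.2.4.8): apply the SAP's existing IGA LOCF rule to treated subjects with a baseline IGA. This also brings in early terminators, so the text should say so.
- **Wording of 7.2**: change all three sentences of the introduction for these tables. Removing only the first would leave the other two still restricting them to the FAS.
- **Linked outputs**: make the same change in Table 7.5.1, Figure 8.6 and the interim IGA and satisfaction analyses in SAP 6.3.1. Figure 8.7 follows from Table 7.2.8.
- **Keep the survey-based FAS** for the PRO tables and the patient-clinician pairings in 7.3.
- **Add to SAP 6.11**: the FAS result for IGA success and satisfaction as a sensitivity analysis, with the number of rated subjects who had no Week-12 survey.

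The cost is SAP text and one population flag, with no new data collection. N will differ between the investigator tables and the PRO tables and needs a footnote. If the reported number without a survey is zero, the results without imputation and the satisfaction results will not change.

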**Table 7.2.1. Site Characteristics**

Domain	(N=xx)
S1: Current workplace	
Private, office-based practice	n (%)
Hospital-based practice	n (%)
S2: Total number of board-certified dermatologists in the practice (including yourself, if applicable)	N, Mean (SD), Median, Min, Max
S3: At present, how many patients with acne vulgaris (AV) do you personally manage in a given month?	N, Mean (SD), Median, Min, Max
S4: How long have you been practicing dermatology, post-residency?	N, Mean (SD), Median, Min, Max
S5: How often do you prescribe broad-spectrum antibiotics (such as doxycycline and minocycline)?	N, Mean (SD), Median, Min, Max
Never (0)	n (%)
Rarely (1)	n (%)
Some of the time (2)	n (%)
Most of the time (3)	n (%)
All of the time (4)	n (%)
S6: How concerned are you about antibiotic resistance with long-term antibiotic use?	N, Mean (SD), Median, Min, Max
Not at all (0)	n (%)
Slightly (1)	n (%)
Somewhat (2)	n (%)
Moderately (3)	n (%)
Extremely (4)	n (%)
S7: How concerned are you about disruption of the microbiome with long-term antibiotic use?	N, Mean (SD), Median, Min, Max
Not at all (0)	n (%)
Slightly (1)	n (%)
Somewhat (2)	n (%)
Moderately (3)	n (%)

Extremely (4)	n (%)	
S8: How important is the role of narrow-spectrum antibiotics (such as sarecycline/Seysara®) in supporting antibiotic stewardship?		N, Mean (SD), Median, Min, Max
Not at all (0)	n (%)	
Slightly (1)	n (%)	
Somewhat (2)	n (%)	
Moderately (3)	n (%)	
Extremely (4)	n (%)	

Note: Data from Clinician DCF. The denominator for the percentage is N which refers to total number of unique sites in PROSES study.

**Table 7.2.2. Study Subject Selection Criteria**

Domain (N=X)	Yes	No
Diagnosed with non-nodular moderate to severe acne vulgaris on the face	n (%)	n (%)
S9Br1. Considered a candidate for sarecycline/Seysara® treatment AND you plan to administer sarecycline/Seysara® treatment	n (%)	n (%)
S9Br2. AT LEAST 9 years of age at the time of initiation of sarecycline/Seysara® treatment	n (%)	n (%)
S9Br3. Able to read and write English	n (%)	n (%)
S9Br4. Able to provide consent (in case of adult patients) or assent (in case of pediatric patients) to participate AND is willing to comply with study procedures	n (%)	n (%)
S9Br5. Currently being treated with any of the following: penicillin, oral retinoids (including isotretinoin and acitretin)	n (%)	n (%)
S9Br6. Among the female subjects: Currently pregnant, lactating or is planning a pregnancy during the study period	n (%)	n (%)
S10r1. Have known resistance to other tetracyclines?	n (%)	n (%)
S10r2. Have another dermatological or physical condition of the face that could interfere with the acne vulgaris clinical evaluations?	n (%)	n (%)
S10r3. Have an history of allergy to tetracycline-class antibiotics, pseudomembranous colitis or antibiotic-associated colitis?	n (%)	n (%)
S10r4. Have a medical chart accessible to complete baseline data collection?	n (%)	n (%)
S11. Is the patient under 18 years of age (9 to 17 years), requiring a legal caretaker for the purposes of this study?	n (%)	n (%)
S12r1. Older than 18 years of age?	n (%)	n (%)
S12r2. Able to read and write English?	n (%)	n (%)
S12r3. The primary caregiver of the study-eligible patient?	n (%)	n (%)

S12r4. Legally able to provide consent to participate in the study and willing to comply with study procedures?	n (%)	n (%)
--	-------	-------

Note: Data from Clinician DCF. The denominator for the percentage is the number of patients with available data (N=X). There are no missing data.

**Table 7.2.3. Patient Clinical Characteristics from Medical Chart**

Character	Baseline (N=x)
M1B: Gender	
Male	n (%)
Female	n (%)
M2: Primary Health Insurance	
Private health insurance	n (%)
Medicaid	n (%)
Medicare	n (%)
Uninsured	n (%)
Other	n (%)
Not available	n (%)
M3r1. Height (in inches)	N, Mean (SD), Median, Min, Max
M3r2. Weight (in lbs/pound)	N, Mean (SD), Median, Min, Max
M5: Waist circumference (in inches)	N, Mean (SD), Median, Min, Max
Body Mass Index (BMI - calculated)	N, Mean (SD), Median, Min, Max
M6: Blood pressure (in mm HG)	
M6r2. Systolic	N, Mean (SD), Median, Min, Max
M6r3. Diastolic	N, Mean (SD), Median, Min, Max
M7: Concomitant (comorbid) conditions	
M7r1. Anxiety	n (%)
M7r2. Anemia or other blood disease	n (%)
M7r3. Asthma	n (%)
M7r4. Atopic dermatitis	n (%)
M7r5. Cancer (of any type)	n (%)
M7r6. Crohn's disease / IBD	n (%)
M7r7. Diabetes	n (%)
M7r8. Depression	n (%)
M7r9. Dyslipidemia/Hyperlipidemia	n (%)
M7r10. Gastroesophageal reflux disease	n (%)
M7r11. Heart disease	n (%)

---

M7r12. Hypertension	n (%)
M7r13. Kidney disease	n (%)
M7r14. Liver damage or disease	n (%)
M7r15. Lung disease	n (%)
M7r16. Osteoarthritis, degenerative arthritis	n (%)
M7r17. Other gastrointestinal disease	n (%)
M7r18. Other	n (%)
M7r18oe A, B, C	n (%)

---

Note: Data from Clinician DCF; X patients had missing data; The denominator for the percentage is the number of patients with available data (N=X)

**Table 7.2.4.1 Clinician Acne Evaluation (IGA) (without imputation)**

Character	Baseline (N=x)	Week 4 (N=x)	Week 8 (N=x)	Week 12 (N=x)
Overall, how is the patient's facial acne right now? (IGA)	S9A N, Mean (SD), Median, Min, Max	P2 N, Mean (SD), Median, Min, Max	P2 N, Mean (SD), Median, Min, Max	P2 N, Mean (SD), Median, Min, Max
Clear (0)	n (%)	n (%)	n (%)	n (%)
Almost clear (1)	n (%)	n (%)	n (%)	n (%)
Mild (2)	n (%)	n (%)	n (%)	n (%)
Moderate (3)	n (%)	n (%)	n (%)	n (%)
Severe (4)	n (%)	n (%)	n (%)	n (%)
Clear/almost clear	n (%)	n (%)	n (%)	n (%)
Moderate / Severe	n (%)	n (%)	n (%)	n (%)
Mild	n (%)	n (%)	n (%)	n (%)
M1A.1: Who did the evaluation of the patient's acne severity?				
Dermatologist	n (%)	n (%)	n (%)	n (%)
Nurse Practitioner	n (%)	n (%)	n (%)	n (%)
Physician's assistant	n (%)	n (%)	n (%)	n (%)
M1A.2: How was the evaluation of acne severity done?				
During in-person patient visit (face-to-face)	n (%)	n (%)	n (%)	n (%)
Via telehealth visit (video)	n (%)	n (%)	n (%)	n (%)

Note: Data from Clinician DCF; X patients had missing data; The denominator for the percentages is the number of patients with available data (N=X)

